#### **9.4.10.4 Pregnancy**

Pregnancy is not considered an SAE or AE. The site will inform [REDACTED] immediately of any case of pregnancy and collect information on any subject who becomes pregnant during the study using the *Unexpected Problems Report Form*.

Subjects who become pregnant will continue to be followed up for scheduled efficacy and safety assessments for the duration of the study.

## 10 SUBJECT COMPLETION / WITHDRAWAL / STOPPING RULES

### 10.1 Completion

A subject will be considered to have completed the study if he or she has completed all the assessments or has experienced an event that precludes further participation in the study.

### 10.2 Withdrawal

A subject **will be** withdrawn from the study for any of the following reasons:

- Lost to follow-up;
- Withdrawal of consent;
- The Principal Investigator believes that for safety reasons (e.g., AE, concurrent illness) that it is in the best interests of the subject to be withdrawn from study participation;
- The subject's attending physician requests that the subject be withdrawn from the study;
- The Principal Investigator or the Sponsor, for any reason, stops the study or stops the subject's participation in the study.

Protocol deviations will not lead to automatic withdrawal unless they indicate a significant risk to the subject's safety. All major protocol deviations must be discussed promptly with the Medical Monitor.

A subject **may be** withdrawn from the study, in consultation with the Medical Monitor, for any of the following reasons:

- Lack of compliance to study procedures;
- A significant protocol deviation or violation;
- Poor visit attendance.

Should a subject decide to withdraw after administration of a study device(s), or should the Principal Investigator decide to withdraw the subject, the Principal Investigator (or designate) will complete and report the observations up to the time of withdrawal.

All subjects who are withdrawn from the study will be requested to come in to complete their next scheduled clinic visit. The next scheduled visit may be brought forward to facilitate this. A complete evaluation at the time of the subject's withdrawal should be made. Additionally, subjects who withdraw from the study will be requested to allow continued safety monitoring, either via telephone interviews or clinic visits, whichever is more appropriate.

The reason and date of withdrawal must be noted on the eCRF. If the reason for withdrawal is an AE or an abnormal laboratory test result, monitoring will continue until resolution or until an appropriate medical judgment concerning the cause or importance has been made. The specific event or test result(s) must be recorded on the eCRF.

[REDACTED]

[REDACTED]

[REDACTED]

[REDACTED]

[REDACTED]

[REDACTED]

[REDACTED]

[REDACTED]

## 11.6 General Considerations

Data will be listed by treatment group and subject number. The safety and efficacy data will be summarized by treatment allocation. Descriptive statistics will consist of mean, standard deviation, minimum and maximum for continuous variables, and frequency and percent for discrete variables.

A full description of the statistical methods planned for this study will be provided in the Statistical Analysis Plan (SAP). The SAP will be finalized and approved by the study Sponsor prior to the last subject's last visit. All programs for data output and analyses will be written in SAS version 9.4 or higher (SAS Institute, Inc., Cary, NC).

[REDACTED]

## 11.7 Effectiveness Analysis

### 11.7.1 Primary Endpoint

Effectiveness of RHA®4 [REDACTED] with [REDACTED] versus control will first be analyzed in a non-inferiority statistical model using the pain felt by the subject during injection. If non-inferiority is achieved, pain felt by the subject during injection will be tested for superiority (i.e., to confirm if RHA®4 [REDACTED] is superior to RHA®4 for reducing pain).

[REDACTED]

Wilcoxon signed-rank test

[REDACTED]

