	
17. Medical or psychiatric conditions that may increase the risk associated with study participation or may interfere with the interpretation of study results or compliance of the subject and, in the judgment of the Investigator, would make the subject inappropriate for entry into this study.
 
18. Clinically significant alcohol or drug abuse, or history of poor cooperation or unreliability.
 
19. Exposure to any other investigational drug/device within 90 days of entering the study.

Device Administration	
[REDACTED]
 
Injection technique: The injection technique (e.g., linear threading, cross hatching, fan like administration, multiple puncture) will be at the discretion of the TI, and will be recorded. The same injection techniques will be used on both sides.
 
[REDACTED]

Blinding	This is a double-blinded study. Subjects and TI will be blinded to treatment allocation.
Randomization	A randomization algorithm will provide equal balancing for the side of the face and the order of injection of study devices [REDACTED]
Visit Procedures	Refer to the Study Summary Tables and the Study Schematic for a schedule of activities.
Anesthetic Effectiveness Evaluations	
 
• Injection Site Pain on each side of the face during injection (primary endpoint)
 
• Injection Site Pain on each side of the face at 15, 30, 45 and 60 minutes post-injection
 
• Duration of anesthetic effect on each side of the face (patient diary)
 

Aesthetic Effectiveness Evaluations	
[REDACTED]
 
[REDACTED]
 
[REDACTED]
 
[REDACTED]
 
 
• [REDACTED]
 

Safety Evaluations	
 
• Adverse Events
 
• Post-injection Common Treatment Response [REDACTED] (30-day patient CTR diary)
 
• [REDACTED]
 

Primary Endpoint	Injection site pain felt during injection of one NLF assessed by the subject immediately following injection with RHA ® 4 [REDACTED] with [REDACTED] compared to the injection site pain felt during injection into the contralateral NLF assessed immediately following injection with RHA ® 4 with lidocaine.

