## **6 TREATMENT ALLOCATION, RANDOMIZATION AND BLINDING**

All subjects who have signed an ICF will receive a 3-digit subject number, starting at 001. Subject numbers will be assigned in ascending order and will be coupled with the site identification number for unique identification of each subject. The subject number will be used to identify the subject throughout the study. Subjects withdrawn from the study will retain their subject number; new subjects will be allocated a new subject number.

Upon qualifying for treatment, subjects will be randomized for the side of the face and the order of injection of study devices (i.e., left or right / 1st or 2nd order).

Subjects will be considered “enrolled” at the time of consent, and will be considered “enrolled and randomized” at the time of randomization. The required sample size is based on “enrolled and randomized” subjects. If an enrolled subject withdraws from the study prior to being randomized, he/she may be replaced.

This is a double-blinded study in which subjects and TIs will be blinded to treatment allocation.

Designated site personnel will secure the randomization/treatment allocation information and any other record of study treatment from potential discovery by the TI or the subject. Any instance where the blind is opened to the TI or subject will be documented in writing.

If it is medically imperative to know what device was injected into the left and right NLF, the TI or study coordinator will contact [REDACTED] to confirm the rationale for unblinding. If appropriate, [REDACTED] and/or the Sponsor will approve unblinding and treatment assignments for that particular subject will be disclosed. The rationale for breaking the code must be recorded in subjects’ medical record and eCRF.

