### 11.7.2 Secondary Endpoints

Secondary endpoint statistical analysis will be performed if the non-inferiority of the primary endpoint is achieved. All statistical inference tests will be performed at the same significance level ( $\alpha$ ) of 0.05.

For categorical and continuous variables, the two groups will be compared using two-sided parametric or non-parametric tests for paired data, as appropriate. Due to the small sample size, normality of the observed distribution will be visually confirmed. If data appear normally distributed, testing will be conducted using the Student t-test, while testing will be conducted with the Wilcoxon signed-rank test if not normally distributed.

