3. TREATMENT ALLOCATION, RANDOMIZATION AND BLINDING

Upon qualifying for treatment, subjects will be randomized for the side of the face and the order of injection of study devices (i.e., left or right / 1st or 2nd order).

Subjects will be considered "enrolled" at the time of consent, and will be considered "enrolled and randomized" at the time of randomization. The required sample size is based on "enrolled and randomized" subjects. If an enrolled subject withdraws from the study prior to being randomized, he/she may be replaced.

This is a double-blinded study in which subjects and TIs will be blinded to treatment allocation.

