4.1.2 Injection Sequence

Upon qualifying for treatment, subjects will be randomized for the side of face and the order of injection (i.e., left or right / 1st or 2nd order).

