6. STATISTICAL METHODS

6.1 Primary Endpoint

The primary endpoint will be the injection site pain during injection into one NLF assessed by the subject immediately following injection with RHA[®] 4- with **during** compared to the injection site pain felt during injection into the contralateral NLF assessed immediately following injection with RHA[®] 4 with lidocaine.

The effectiveness of RHA[®] 4- with will be demonstrated if the injection site pain during injection assessed by the subject immediately following injection with RHA[®] 4- with is statistically non-inferior to the injection site pain felt during injection of the contralateral NLF assessed by the subject immediately following injection with RHA[®] 4 with

The primary endpoint will use the PP population, a paired design and will be analyzed using hypothesis test.

For achieving non-inferiority, the observed p value must be ≤ 0.05 , taking account of the non-inferiority margin (i.e., 10mm difference in Pain VAS between the two treatment groups).

In case of non-inferiority, for achieving superiority of RHA[®] 4- with with over RHA[®] 4 with lidocaine in terms of reducing pain, the observed p value must be ≤ 0.05 .

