6.7 Effectiveness Analysis

6.7.1 Primary Endpoint

Effectiveness of RHA[®]4- with versus control will first be analyzed in a noninferiority statistical model using the pain felt by the subject during injection. If non-inferiority is achieved, pain felt by the subject during injection will be tested for superiority (i.e., to confirm if RHA[®] 4- is superior to RHA[®] 4 for reducing pain).

Wilsoner signed work toot		
wilcoxon signed-rank test		

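### Injection order and side are randomized and balanced, but no legible test uses them: confirm whether the SAP adjusts and, if not, pre-specify it (low-priority efficiency point)

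*Protocol*

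**What the plan says.** **Randomization.** The Protocol synopsis states: "A randomization algorithm will provide equal balancing for the side of the face and the order of injection of study devices". Protocol section 6 says: "Upon qualifying for treatment, subjects will be randomized for the side of the face and the order of injection of study devices". SAP sections 3 and 4.1.2 repeat this, the latter as "subjects will be randomized for the side of face and the order of injection". Any detail on blocks or strata is not legible.

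**Primary analysis.** SAP 6.1 says: "The primary endpoint will use the PP population, a paired design". It sets a 10 mm margin and a p-value threshold of 0.05; the sidedness of the non-inferiority test is not legible. In Protocol 11.7.1 the words "Wilcoxon signed-rank test" stand alone between redacted blocks. In SAP 6.7.1 the same test name survives as a table fragment. Whether it is the main, fallback or sensitivity test cannot be read. Both sections also refer to a statistical model for non-inferiority without legible detail.

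**Secondary analysis.** Protocol 11.7.2 calls for two-sided tests for paired data after a visual check of normality. If the data look normal, "testing will be conducted using the Student t-test, while testing will be conducted with the Wilcoxon signed-rank test if not normally distributed".

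**What cannot be read.** The SAP contents list a section 6.7.2 on secondary endpoints, but its text is absent. After SAP 6.8.1 there are table fragments, by position apparently Appendix A, in which the signed-rank test is the only test named. The SAP states that it prevails over the Protocol where they differ.

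**The concern.** If the first injection hurts more or less than the second whatever the device, each test-minus-control difference shifts up or down by that amount according to order. A left-right difference acts the same way. Balance cancels these shifts in the mean, but a signed-rank or paired t-test leaves them in the variance of the paired differences. An analysis that uses order and side removes them without extra data.

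The trial treats at most 30 subjects, and under Protocol 11.7.2 secondary testing goes ahead only if primary non-inferiority is shown. A modest loss of power is therefore worth avoiding where it costs little. A second stake is that the primary uses the per-protocol set, where exclusions can disturb the balance that randomization gave.

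**Working it through.** **1. The plan's own figure.** The documents give n = 30 (maximum), but the SD, power and order effect behind it are not legible, so 30 cannot be reproduced. Back-solving SD = 10 x sqrt(n) / (z_alpha + z_beta), with true difference 0:

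- One-sided 5%: SD up to 22.0 mm (80% power) or 18.7 mm (90%).
- One-sided 2.5%: SD up to 19.6 mm or 16.9 mm.

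An assumed SD of 20 mm is therefore in a plausible range, but it is an assumption.

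**2. Model.** d = tau + o x lambda + s x sigma + error. Here d is test minus control; o = +1 if test is first, -1 if control is first; s = +1 if test is on the left, -1 if on the right; lambda is the first-minus-second pain difference and sigma the left-minus-right difference. Under balance the mean of d is tau, and its variance is inflated by 1 + (lambda^2 + sigma^2)/SD^2. With SD 20 and sigma 0:

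- 5 mm: 1 + 25/400 = 1.06
- 10 mm: 1 + 100/400 = 1.25
- 15 mm: 1 + 225/400 = 1.56

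**3. Power by simulation.** 40,000 runs per cell; n = 30 in order-by-side cells of 8/7/7/8; true difference 0; margin 10 mm; one-sided 5%; residual SD 20 mm; normal errors; Monte Carlo error about 0.5 point.

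| Order effect | Signed-rank | van Elteren | Gain | Paired t | Linear, order + side | Gain |
|---|---|---|---|---|---|---|
| 0 mm | 83.1% | 82.0% | -1.1 | 85.0% | 84.9% | -0.1 |
| 5 mm | 81.1% | 81.8% | +0.7 | 83.3% | 84.5% | +1.2 |
| 10 mm | 76.6% | 81.7% | +5.1 | 79.5% | 84.6% | +5.1 |
| 15 mm | 68.2% | 81.7% | +13.5 | 72.7% | 84.6% | +11.9 |

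Adding a 5 mm side effect to the 10 mm order effect gives signed-rank 74.6%, van Elteren 81.7% and linear 84.7%.

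**4. Validity.** Under balance, signed-rank type I error at the margin is 3.1% with a 10 mm order effect and 1.8% with 15 mm, against a nominal 5%.

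**5. Sensitivity.**

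- *One-sided 2.5%* (20,000 runs), paired t v linear: 75.7 v 75.5% at 0 mm, 73.6 v 75.6% at 5 mm, 67.5 v 75.4% at 10 mm.
- *Other residual SDs*, 10 mm effect, paired t v linear: SD 12, 98.8 v 99.7%; SD 15, 94.0 v 97.3%; SD 25, 64.1 v 68.9%.
- *20 mm taken as the total SD of the paired differences*, 10 mm effect: signed-rank 84.8 v van Elteren 90.0%; paired t 87.3 v linear 92.1%.
- *VAS clipped to 0-100 and rounded*, nominal 10 mm effect: at mean 25, signed-rank 86.3 v van Elteren 89.0% and paired t 87.6 v linear 90.9%; at mean 40, 82.1 v 85.8% and 84.1 v 88.4%. The gain is about 3 to 4 points.
- *Heavy tails* (t, 3 df, SD 20) at 0/5/10/15 mm: signed-rank 96.2/94.8/90.2/80.5%; van Elteren 95.4/95.3/95.3/95.5%; linear about 88% throughout.
- *Secondary-type comparison*, two-sided 5%, true difference 10 mm, paired t v linear: 75.3 v 75.1% at 0 mm, 73.5 v 75.4% at 5 mm, 67.4 v 75.4% at 10 mm.

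**6. Per-protocol imbalance.** Bias = lambda x (n1 - n2)/(n1 + n2). The splits are illustrative, with a 10 mm order effect:

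- 14 v 11: 10 x 3/25 = 1.2 mm; signed-rank type I error 6.0% or 1.7% by direction, adjusted 5.0 to 5.2%.
- 14 v 12: 10 x 2/26 = 0.8 mm; 5.0% or 2.2%.

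**The case against.** The strongest reply is that nothing is shown to be wrong, and most of it stands.

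- *A reader might infer that the plan omits the adjustment.* The documents do not support that. The primary text is redacted around the test name. For the secondaries, Protocol 11.7.2 is readable, but the SAP prevails and its section 6.7.2 is absent. Omission is unproven for both.
- *A reader might infer that the unadjusted test is biased or that the trial is underpowered.* Under balance the test is valid and conservative, and the sample-size basis is redacted. If planning used the total SD of paired differences, an order effect is already counted in it, and unadjusted power is no lower than with no order effect.
- *The gain depends on an order effect that no document reports.* At 5 mm it is about 1 point or less; 5 points needs an effect as large as the whole margin. The design also limits side differences: equal WSRS grade on both sides, the same technique, and only the supplied needle.
- *A reader might conclude that a linear model should replace the signed-rank test.* With heavy-tailed differences it loses about 8 points to signed-rank with no order effect and about 2 at 10 mm. Each planned test should therefore be paired with its own adjusted counterpart.

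What survives is that the trial randomizes two factors, no readable test uses them, and using them costs little.

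**Conclusion.** The point holds as a low-priority query about efficiency. Order and side are randomized and balanced, and no legible test uses either; whether text that cannot be read already does so is unknown.

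If there is no adjustment, the loss is negligible for an order effect up to about 5 mm, about 5 power points at 10 mm, and 12 to 14 at 15 mm. These figures rest on assumed values: 30 analysed subjects, residual SD 20 mm, normal errors, true difference 0 and one-sided 5%. Only the margin and the maximum sample size come from the documents. Adjustment also protects against a bias of about 1 mm if per-protocol exclusions modestly unbalance a 10 mm order effect. It does not remove carry-over, where the first device changes the response to the second.

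**What to change.** **First, confirm** whether SAP 6.7.1, SAP 6.7.2 or Appendix A already uses order and side. If so, no change is needed.

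**If not, pre-specify before unblinding** the like-for-like adjusted version of each planned test:

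- *Where the signed-rank test is planned:* a van Elteren test of first-minus-second VAS, test-first against control-first, stratified by the side injected first. The two order groups differ by 2 x tau, so use a 20 mm shift (2 x 10 mm) for non-inferiority and 0 for superiority.
- *Where the paired t-test is planned:* a linear model of the test-minus-control difference on order and side, each coded +1/-1. The intercept is the treatment difference; read it and its interval against 10 mm for non-inferiority and 0 for superiority, at the SAP's existing level.

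For paired secondary comparisons use the same counterparts against 0. Keep the unadjusted test as sensitivity.

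**Cost:** SAP wording and a few lines of SAS. The linear model spends two degrees of freedom (85.0% to 84.9% with no order effect). With no order effect, van Elteren gives up about 1 point at one-sided 5% (83.1% to 82.0%) and 2.5 points at one-sided 2.5% (73.5% to 71.0%).

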### 11.7.2 Secondary Endpoints

Secondary endpoint statistical analysis will be performed if the non-inferiority of the primary endpoint is achieved. All statistical inference tests will be performed at the same significance level ( $\alpha$ ) of 0.05.

For categorical and continuous variables, the two groups will be compared using two-sided parametric or non-parametric tests for paired data, as appropriate. Due to the small sample size, normality of the observed distribution will be visually confirmed. If data appear normally distributed, testing will be conducted using the Student t-test, while testing will be conducted with the Wilcoxon signed-rank test if not normally distributed.

### 11.8 Safety Analysis

The SAFT Population will be used to summarize the safety of the study devices and will consist of all treated subjects. The primary safety analysis is the calculation of the incidence of CTRs and adverse events in the study period. Point estimates for all CTRs, AEs and SAEs will be presented and two-sided exact 95% confidence intervals will be calculated for the overall incidence of AEs and SAEs. Tables will be generated which summarize AEs by investigator assessments of both relationship to treatment and severity.

#### 11.8.1 Adverse Events (AEs)

Safety outcomes will be incidence rate of AEs, including UADEs, types of AEs and their relationship to study treatment. Severity and relationship to study treatment will be assessed and recorded.

AEs will be coded using the Medical Dictionary for Regulatory Activities (MedDRA) dictionary. These events, irrespective of relationship to study medication, will be summarized by MedDRA system organ class (SOC) and MedDRA preferred term (PT). The number of subjects reporting an AE, the number of AEs, and percentages of subjects in each category will be summarized. AEs by severity and relationship to study will be summarized in a similar way. Serious AEs will be summarized separately. Specifically, the following AE incidence tables will be provided:

- All and possibly\* related AEs sorted by SOC
- All and possibly\* related AEs sorted by decreasing frequency
- SAEs: All and possibly\* related SAEs sorted by seriousness criterion
- SAEs: All and possibly\* related SAEs sorted by SOC
- UADEs: All and possibly\* related UADEs sorted by SOC
- Death: All and possibly\* related deaths sorted by SOC

\* *definitely probably, possibly*

Incidence rates with two-sided exact 95% confidence intervals will be calculated for the overall incidence of AEs and SAEs

Statistical analysis will also be performed to evaluate the potential impact of the injection technique on the safety data.

## **12 ETHICAL ASPECTS**

### **12.1 Informed Consent**

This study will be conducted in compliance with 21 CFR Part 50 for informed consent. Written informed consent will be obtained from each subject before any procedures or assessments are done and after the aims, methods, anticipated benefits, and potential hazards are explained. It will also be explained to the subject that they are free to refuse entry into the study and free to withdraw from the study at any time without prejudice to future treatment.

Written and/or oral information about the study in a language understandable by the subject will be given to all subjects. The information provided must include an adequate explanation of the aims, methods, anticipated benefits, potential hazards, compensation and/or honoraria, and insurance arrangements in force.

The subject's willingness to participate in the study will be documented in writing on a consent form, which will be signed by the subject with the date and time of that signature indicated. The site will keep the original consent forms and copies will be given to the subjects.

See also Section 9.1.

### **12.2 Health Authorities and IRBs**

The Principal Investigator will ensure that the conduct of the study conforms to the Declaration of Helsinki, the Belmont Report, and with national laws and regulations for clinical research.

Before starting this study, the protocol will be submitted to the FDA and central IRB for evaluation. As required, the study will not start before the IRB and the FDA give approval.

